The primary endpoints of the study are PROMIS® pain intensity and PROMIS® pain interference t-scores. Each endpoint will be analyzed separately using an ANCOVA model for each. Using the MITT population for analysis, the t-score of the PROMIS® outcome at 7 days post-URS will be the dependent variable and treatment arm and pre-treatment (baseline) PROMIS t-score will be independent variables. The primary comparison of interest is treatment arm. The baseline adjusted mean pain score at 7-days will be reported by arm with the 97.5% confidence interval and a type-3 F-test will test the hypothesis that pain differs between the two treatment groups. Each endpoint modeled will test the effect of treatment arm adjusting for baseline with a type I error of 2.5% for an overall study type I error of 5%.

An analysis in the per-protocol population will be assess the robustness of the effect found in the primary analysis. Additionally, a multivariable model will be considered to account for other patient or surgical variables that may be unbalanced between the arms including timing of stent removal or stone location.

Analysis of the Secondary Endpoints

Additional health-related quality of life endpoints including PROMIS® Pain scores at 4 weeks will be analyzed with similar models described for the primary endpoint. A linear mixed model will be used to compare LURN SI-10 scores at 7 days and 4 weeks between treatment arms. Each analysis will report means with 95% confidence intervals at each time for each arm with a model based type-3 F-test comparing treatment arms.

Healthcare utilization within 30 days of URS will be assessed using a composite endpoint. The composite healthcare utilization metric within 30 days will be a composed score based upon utilization by the patient with each patient assigned a score based upon the highest utilization level that they participate in with levels defined in decreasing order:

5. Hospitalization and ICU care
4. Unplanned hospitalization
3. Emergency department visit
2. Ambulatory encounter: Clinic visit
1. Ambulatory encounter: Phone call or message

We will compare the composite score ranking between the treatment arms using a WinRatio analysis using the unmatched approach.(20) The median composite score for each arm will be reported, along with the WinRatio and associated 95% confidence interval and p-value.

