In addition to the WinRatio, our second composite analysis will include healthcare utilization and PROMIS® Pain. Additionally, we will use a composite score ranking of healthcare utilization similar to the WinRatio plan and add the PROMIS® Pain scores to the analysis using DOOR. The probability that a randomly selected patient will have a better DOOR if assigned to the silicone stent will be estimated.(21) The WinRatio and DOOR composite healthcare utilization metric ratios' sizes and directions will be compared.

The number and proportion of patients who are prescribed opioid medications will be reported by arm and compared using a chi-square test.

Satisfaction score assessed using the ICIQ-S will be summarized at 7 days and 4 weeks by arm with means and standard deviations. A repeated measures model will be used to test if satisfaction differed at either time between treatment arms using an interaction of time and arm.

Section 12: DATA AND SAFETY MONITORING

The DSMC will consist of the MUSIC ROCKS Program Manager, Program Director, Statistician, and other members of the MUSIC ROCKS team. This committee is responsible for monitoring the safety and data integrity of the study.

Each performance site's local study team is required to meet virtually with the DSMC and BLUES study team every six months if it is determined by the DSMC and/or Principal Investigator that a virtual meeting is necessary. The discussion may include matters related to the safety of study participants (Serious Adverse Event, Adverse Event and Unanticipated Problem reporting), completeness, validity and integrity of the study data, enrollment rate relative to expectations, characteristics of participants, retention of study participants, and adherence to the protocol (potential or real protocol deviations). If there are no concerns around any of the aforementioned items, the principal investigator and/or the DSMC may decide that a meeting is unnecessary and if so, a progress summary communication will serve in its place. Additionally, a member of the BLUES study team will send a communication summarizing current progress to each site on a monthly basis. These communications will consist of 1) any identified Serious Adverse Events and necessary follow-up, 2) enrollment rate relative to expectations, and 3) any identified protocol deviations, unanticipated problems, and recommendations to prevent additional instances.

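### The planned size comparison of the WinRatio with the DOOR result mixes scale, tie handling and an added pain outcome, and the plan fixes none of the three

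*Combined protocol and SAP*

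**What the plan says.** **WinRatio.** Section 11.4 (Analysis of the Secondary Endpoints) builds one ordinal utilization score, with "each patient assigned a score based upon the highest utilization level that they participate in". Five levels are listed, from a phone call or message up to hospitalization with ICU care. No level is listed for a patient with no encounter. The arms are compared "using a WinRatio analysis using the unmatched approach", and the reporting rule is: "The median composite score for each arm will be reported, along with the WinRatio and associated 95% confidence interval and p-value". How ties are treated is not stated.

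**DOOR.** Section 11.4 (Exploratory Analyses) says that "our second composite analysis will include healthcare utilization and PROMIS® Pain" and that the analysis will "add the PROMIS® Pain scores to the analysis using DOOR". The quantity to be estimated is a probability: "The probability that a randomly selected patient will have a better DOOR if assigned to the silicone stent will be estimated". The text does not say which pain score is used, at which time, or where pain ranks relative to utilization.

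**The comparison.** The next sentence calls both results ratios of a utilization metric and says that their "sizes and directions will be compared". The Section 2 synopsis and Section 5.3 list a composite score difference between the two methods as an exploratory endpoint and objective. Section 5.4 describes the DOOR endpoint as a healthcare utilization composite and does not mention pain.

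**Purpose.** The exploratory section says the aim is to assess the plausibility of two composite measurement plans, with future trials in view.

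**The concern.** The two results differ in three ways, and the plan separates none of them.

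- **Scale.** A win ratio with no treatment effect is 1. A probability of a better outcome with no effect is 0.5 when ties are split. Read literally, the difference named in the synopsis would be 1 − 0.5 = 0.5 when the stents are identical.
- **Ties.** By the usual conventions, the win ratio is wins over losses, so tied pairs drop out, while the DOOR probability counts half of each tie. With so few utilization levels, ties will be common.
- **Content.** In Section 11.4 the DOOR contains PROMIS pain and the WinRatio does not.

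At stake is what the trial can say about its two candidate composites. If one result looks larger, the reader cannot tell whether the method, the ties or the pain scores caused it.

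**Working it through.** The documents give no figure for either composite, so there is nothing to reproduce. What follows is an illustration.

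**Input from the documents.** The pain effect is 5 points with SD 10 (Section 11.2), so d = 5/10 = 0.5 SD.

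**Assumed inputs, not in the documents.** Utilization proportions, ordered none / phone / clinic / ED / hospital / ICU; the level for none is added here.

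- Non-silicone: 0.70 / 0.15 / 0.07 / 0.05 / 0.025 / 0.005
- Silicone: 0.78 / 0.11 / 0.05 / 0.04 / 0.018 / 0.002

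**Formulas.** W, L and T are the probabilities that a random silicone/non-silicone pair is a win, loss or tie for silicone.

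- WinRatio = W/L
- DOOR probability = W + T/2
- Win odds (the DOOR probability as odds) = (W + T/2)/(L + T/2)

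**Step 1: utilization only.** Summing over all pairs of levels:

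- W = 0.2340 + 0.0165 + 0.0040 + 0.0012 + 0.0001 = 0.2558
- L = 0.1540 + 0.0165 + 0.0042 + 0.0010 + 0.0001 = 0.1758 (terms rounded)
- T = 1 − 0.2558 − 0.1758 = 0.5685 (from unrounded values), so 57% ties
- WinRatio = 0.2558/0.1758 = 1.46
- DOOR probability = 0.2558 + 0.2842 = 0.540
- Win odds = 0.540/0.460 = 1.17

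The patients, the outcome and the ranking are the same, so the gap between 1.46 and 1.17 comes from tie handling alone.

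**Step 2: add pain.** Pain is treated as a continuous tie-breaker independent of utilization (an assumption). The chance that it favors silicone within a tied pair is Φ(d/√2).

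| Pain effect | Φ(d/√2) | DOOR probability | DOOR odds | WinRatio |
|---|---|---|---|---|
| 0.5 SD better on silicone | 0.638 | 0.2558 + 0.5685 × 0.638 = 0.619 | 1.62 | 1.46 |
| None | 0.500 | 0.540 | 1.17 | 1.46 |
| 0.5 SD worse on silicone | 0.362 | 0.2558 + 0.5685 × 0.362 = 0.461 | 0.86 | 1.46 |

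In the first row, 1.62 looks close to 1.46. The net difference of about +0.17 is a shift of −0.28 from tie handling (1.46 to 1.17) and +0.45 from pain (1.17 to 1.62). In the last row even the directions disagree, and pain alone is the cause.

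**Step 3: range over tie shares.** Fix the WinRatio at 1.50, so that L = (1 − T)/2.5 and W = 1.5L.

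| Ties | W | L | DOOR probability | Win odds |
|---|---|---|---|---|
| 20% | 0.48 | 0.32 | 0.58 | 1.38 |
| 50% | 0.30 | 0.20 | 0.55 | 1.22 |
| 70% | 0.18 | 0.12 | 0.53 | 1.13 |

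The gap grows with the tie share. In a separate set of assumed distributions, with 20%, 50% or 70% of control patients having no encounter and proportional-odds shifts of 1.0 to 2.0, ties ran from 29% to 59%.

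**The case against.** **The plan's word for both results is ratios, so the DOOR may be meant as odds.** That is possible, but no conversion is stated. It also would not close the gap: on the same utilization data the odds are 1.17 against a WinRatio of 1.46, before pain enters.

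**Direction is still informative.** This stands. Each result can be read against its own null. A reader might infer that the whole planned comparison is empty; the documents do not support that, since the plan compares directions as well as sizes. What is lost is the ability to attribute a disagreement.

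**The plan does not choose a composite by size.** This also stands. A reader might infer that the composite with the larger number would be adopted. Section 11.4 speaks only of assessing plausibility and contains no selection rule.

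**The tie rules are not in the plan.** Correct. Dropping ties and counting half of them are the usual conventions for the two methods. The defect in the plan is that no rule is stated. The 57% is also the tie share for utilization alone; in the DOOR with pain, many of those ties would be broken, and in step 2 all of them are.

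**The numbers are invented.** The utilization proportions are assumed, and pain may well be correlated with utilization. The illustration shows that the mechanism can be large, not what this trial will find.

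**Conclusion.** The point holds at low severity. The text shows directly that a ratio on utilization is to be compared in size with a probability on utilization plus pain, with no conversion, and that Sections 5.4 and 11.4 describe the DOOR differently. The tie element rests on the usual definitions of the two methods. Under the assumptions shown, tie handling alone separates 1.46 from 1.17, and a pain effect of 0.5 SD in either direction carries the DOOR odds from 0.86 to 1.62 with the WinRatio unchanged. A size difference therefore cannot show what either composite contributes.

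This is an under-specified exploratory comparison. No part of the primary analysis, the type I error control or the sample size depends on it, and the WinRatio as a secondary analysis in its own right is not called into question.

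**What to change.** - Keep the planned WinRatio, and report the share of tied pairs beside it.
- For the comparison, put both composites on one tie-counting scale, either P(better) + 0.5 P(tie) or win odds, with confidence intervals.
- Compute that measure twice, for utilization alone and for utilization plus PROMIS pain. The difference between the two then isolates what pain adds.
- State the tie rule, the score for a patient with no encounter, which PROMIS pain score and time point enter the DOOR, and where pain ranks.
- Reconcile Sections 5.4 and 11.4 on whether pain is in the DOOR, and align the synopsis and Section 5.3 wording of a score difference with the chosen scale.

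The cost is a short clarification of the text and a few extra lines of analysis on data already being collected. No change to conduct or sample size is needed.

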Immediate. Based upon prior RCT outside of the United States, the use of silicone ureteral stents has the potential to decrease pain and LUTS after URS.(12) Decreased pain and LUTS after URS secondarily could decrease the rate of ambulatory healthcare utilization, opioid prescriptions, postoperative ED visits, and unplanned hospitalizations. It could also decrease the number of days required to miss work due to recovery.

Long-range. Decreased pain and LUTS after URS secondarily could decrease a patient's exposure to opioid analgesia postoperatively. Less patient requirements for opioid analgesia could decrease the incidence of new persistent long-term use of opiates in these patients.

Section 5: STUDY OBJECTIVES**Section 5.1: Primary Objectives**

1. To determine the health-related quality of life and symptoms in patients with urinary stone disease stented with silicone or polyurethane stents at ureteroscopy.

Section 5.2: Secondary Objectives

1. To compare 30-day emergency department visits and hospitalization rates between study arms
2. To compare rates and intensity of ambulatory healthcare encounters after ureteroscopy and stenting between study arms
3. To compare stone-free rates between study arms
4. To compare abnormal imaging findings after ureteroscopy and stenting between study arms

Section 5.3: Exploratory Objectives

1. To compare days taken off work by patient between study arms
2. To compare days taken off work by caregiver between study arms
3. To compare Ecological Momentary Assessments (EMA) measured via daily text message for 10 days between study arms
4. To compare Composite score difference between Winratio and Desirability Of Outcome Ranking (DOOR) between study arms
5. To compare number of patients receiving opioid prescriptions between study arms
6. To compare ICIQ-s score at 7 days between study arms
7. To compare ICIQ-s score at 4 weeks between study arms

Section 5.4: Endpoints

- Primary Efficacy Endpoint(s):
 - Silicone stent placement will be associated with significantly improved PROMIS® scores of pain intensity and interference at 7 days compared to non-silicone stent placement.
- Secondary Efficacy Endpoint(s):
 - Silicone stent placement will be associated with equivalent PROMIS® scores of pain intensity and interference at 4 weeks compared to non-silicone stent placement.

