 - Silicone stent placement will be associated with significantly improved NIH LURN SI-10 scores from baseline at 7 days compared to non-silicone stent placement.

- Silicone stent placement will be associated with equivalent difference in NIH LURN SI-10 scores from baseline at 4 weeks compared to non-silicone stent placement.
- Silicone stent placement will be associated with improved composite healthcare utilization metric within 30 days compared to non-silicone stent placement.
 - Hospitalization and ICU care
 - Unplanned hospitalization
 - Emergency department visit
 - Ambulatory encounter: Clinic visit
 - Ambulatory encounter: Phone call or EMR message
- Silicone stent placement will be associated with equivalent abnormal imaging findings within 60 days compared to non-silicone stent placement.
 - New/worsening hydronephrosis
- Silicone stent placement will be associated with equivalent stone-free rates within 60 days compared to non-silicone stent placement.
- Tertiary/Exploratory Endpoint(s):
 - Silicone stent placement will be associated with significantly improved Ecological Momentary Assessment (EMA) scores measured via daily text message for 10 days compared to non-silicone stent placement.
 - Daily visual analog scale survey for pain
 - PROMIS® daily ability to participate in social roles and activities score
 - Silicone stent placement will be associated with significantly less number of days taken off work by patient.
 - Silicone stent placement will be associated with significantly less number of days taken off work by caregiver.
 - Silicone stent placement will be associated with significantly improved composite healthcare utilization metric within 30 days compared to non-silicone stent placement using Desirability of Outcome Rating (DOOR) method
 - The WinRatio and DOOR composite healthcare utilization metric ratios' sizes and directions will be compared.
 - Silicone stent placement will be associated with significantly less number of opioid prescriptions received.
 - Silicone stent placement will be associated with significantly improved ICIQ-S scores at 7 days compared to non-silicone stent placement.
 - Silicone stent placement will be associated with significantly improved ICIQ-S scores at 4 weeks compared to non-silicone stent placement.

Section 6: PATIENT ELIGIBILITY

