A clinically meaningful change in pain PROMIS® score is between 4 and 6 and the standard deviation of the score is 10(16-18). Assuming a 5 t-score PROMIS® pain point difference between 2 arms and a standard deviation of 10, a t-test including 101 patients per arm has 90% power with a 2-sided alpha = 0.025. Assuming a 10% loss-to-follow-up, accrual of 224 study treated patients (112 patients per arm) is planned. Our planned analysis does not match this calculation because we will adjust for the baseline pain to ensure any imbalance prior to surgery is accounted for. However, this power calculation, by ignoring the adjustment of baseline pain, is accurate if the correlation of baseline pain with our outcome is 0. If the correlation is greater than 0, then we will have more power than described.(19)

Section 11.3: Populations for Analyses

Modified Intent-to-Treat (m-ITT) Population: All participants eligible and randomized who complete the pain intensity and pain interference questionnaire between 7-10 days post-URS will be included.

Subjects will be analyzed by assigned treatment at randomization. This is the main population for efficacy analyses.

Per-Protocol Population: All Patients eligible and randomized patients who complete the pain intensity and pain interference questionnaire between at 7 days post-URS will be included per treatment arm received. This second population will be used to assess the robustness of the primary and secondary efficacy outcomes.

Safety Population: All patients who are randomized and receive a stent will be define the safety population and used for all safety analyses. Subjects will be analyzed by assigned treatment arm.

Section 11.4: Statistical Analyses

General Approach

Descriptive statistics for the study population will be reported using frequentist statistics. In general, continuous measures will be reported using means and standard deviations or medians and the interquartile range as the distribution warrants. Categorical variables will be reported as counts and proportions.

Analysis of the Primary Efficacy Endpoints

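### The exploratory ICIQ-S analysis tests the arm-by-time interaction, which asks whether the arm difference changes, not whether it exists at 7 days or 4 weeks

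*Combined protocol and SAP*

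**What the plan says.** ICIQ-S satisfaction is an exploratory endpoint. Section 5.3 lists a separate between-arm comparison for each time; the first is "To compare ICIQ-s score at 7 days between study arms", and a matching objective covers 4 weeks. Section 5.4 states a directional expectation for each time. For 7 days it reads "Silicone stent placement will be associated with significantly improved ICIQ-S scores at 7 days compared to non-silicone stent placement"; the expectation for 4 weeks is the same, with only the time changed.

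Section 11.4, Exploratory Analyses, gives the analysis in two sentences. The first is descriptive: "Satisfaction score assessed using the ICIQ-S will be summarized at 7 days and 4 weeks by arm with means and standard deviations". The second specifies a repeated measures model to "test if satisfaction differed at either time between treatment arms using an interaction of time and arm". No arm main effect, contrast at a single time or joint test is named for ICIQ-S, there or elsewhere. For the secondary scores, by contrast, Section 11.4 asks for means with confidence intervals at each time, together "with a model based type-3 F-test comparing treatment arms".

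**The concern.** The stated question is whether the arms differ at 7 days or at 4 weeks. The stated tool answers another question: whether the size of the arm difference changes between those times. The two come apart in both directions. A steady benefit makes the interaction zero. A benefit at one time that reverses at the other makes it large, so a significant interaction would not by itself show that silicone is better.

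The pattern the test handles worst, benefit of similar size at both times, is consistent with what Section 5.4 predicts. At stake are the ICIQ-S p-value and any conclusion drawn from it.

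**Working it through.** **Setting up the test.** Let d1 and d2 be the standardized arm differences (silicone minus non-silicone) at 7 days and 4 weeks.

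- Question in Sections 5.3, 5.4 and 11.4: is d1 or d2 different from zero? The null is d1 = d2 = 0.
- Interaction with two times: the contrast is d1 − d2. The null is d1 = d2.

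If d1 = d2 = d, the contrast is zero whatever the value of d, so the test rejects at its alpha level. This is algebra and needs no assumed figure.

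**Scale for an illustration.** The documents give no effect size, SD, alpha or power for ICIQ-S. The only planning figures are for the PROMIS pain endpoints in Section 11.2: for a difference of 5 points and an SD of 10 (0.5 SD), the plan states that "a t-test including 101 patients per arm has 90% power with a 2-sided alpha = 0.025". That figure reproduces. The normal approximation gives 100 per arm, and the noncentral t gives 90.1% power at 101 and 89.8% at 100. The planned 112 per arm less 10% loss leaves 112 × 0.90 = 100.8, or about 101.

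Assumed here for ICIQ-S (not in the documents): n = 101 per arm with both scores, differences of 0.3 and 0.5 SD, within-patient correlation ρ of 0.3, 0.5 and 0.7, and two-sided alpha 0.05.

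**Formulas** (SD = 1, normal theory):

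- Contrast at one time: z = d / √(2/n). At d = 0.5, 0.5/√(2/101) = 3.55, power 94.4%. At d = 0.3, z = 2.13, power 56.8%.
- Interaction: z = (d1 − d2) / √(4(1 − ρ)/n). For 0.5 then 0.25 at ρ = 0.3, 0.25/√(2.8/101) = 1.50, power 32.4%.
- Joint 2-df test of d1 = d2 = 0: noncentrality (n/2)(d1² + d2² − 2ρ·d1·d2)/(1 − ρ²). For 0.5 then 0.25 at ρ = 0.5, 50.5 × 0.1875/0.75 = 12.6, power 89.9%.

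**Rejection rates (%)**; entries with slashes are for ρ = 0.3 / 0.5 / 0.7:

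| d1, d2 (SD) | Interaction | Contrast at 7 days, 4 weeks | Joint 2-df |
|---|---|---|---|
| 0.5, 0.5 | 5.0 / 5.0 / 5.0 | 94.4, 94.4 | 98.3 / 96.5 / 94.2 |
| 0.3, 0.3 | 5.0 / 5.0 / 5.0 | 56.8, 56.8 | 65.5 / 58.9 / 53.3 |
| 0.5, 0.25 | 32.4 / 42.7 / 63.1 | 94.4, 42.7 | 91.2 / 89.9 / 92.1 |
| 0.5, 0 | 85.2 / 94.4 / 99.6 | 94.4, 5.0 | 92.6 / 96.5 / 99.6 |

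A simulation of 10,000 trials at ρ = 0.5 gave interaction rejection rates of 5.3% for (0.5, 0.5) and 94.3% for (0.5, 0), in line with the formulas.

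**Could a baseline score change this?** A third time point would alter the algebra, and Section 8.3 contains a run-on phrase that places the word baseline beside ICIQ-S. But the analysis names only the two post-operative times, and the ICIQ-S items in Figure 1 ask about surgery already done. A baseline does not rescue the test.

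**The case against.** The best defence is that the interaction is mentioned only as a model term, included so that arm differences can be estimated separately at each time. On that reading the model is right and the wording loose. The ICIQ-S sentence does not say this, though. It makes the interaction the means of testing. The daily text-message (EMA) analysis in Section 11.4 does list arm, day and their interaction as fixed effects, and the secondary-endpoint text names a test of arm. If contrasts at each time were intended, the same one-sentence change would say so.

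Three limits stand in full.

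- **Consequence.** A reader might infer that a sustained benefit would be hidden from the report. The documents do not support that: means and SDs by arm at both times are planned, so a steady benefit would be visible.
- **Scope.** A reader might infer that the named test is generally powerless. It is not. Section 5.4 expects benefit at both times but does not say by equal amounts. Section 4.3 says stents are often out within 1 to 3 weeks, and Section 5.4 expects equivalent pain and LURN SI-10 results at 4 weeks. A fading difference is plausible, and the interaction can detect one that fades fully.
- **Borrowed figures.** The 0.5 SD and 101 per arm belong to the PROMIS calculation and are not planned ICIQ-S power. The 2.5% alpha is assigned to the two primary endpoints and does not carry over.

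**Conclusion.** The ICIQ-S test is wrong as written, and the point is minor. The mismatch between question and test follows from the algebra alone. The power figures rest on the assumptions listed: if the benefit is equal at both times, the interaction rejects 5% of the time, whereas a contrast at one time has about 57% (0.3 SD) to 94% (0.5 SD) power. If the benefit halves from 0.5 SD, the interaction has 32% to 63% power against about 90% to 92% for a joint test. If it disappears by 4 weeks, the interaction has 85% or more.

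Only the formal ICIQ-S test and its p-value are affected. It would be going too far to read this as a threat to the trial's main conclusion: the endpoint is exploratory and has no part in the primary test, the sample size or the stopping rule.

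**What to change.** Keep the repeated measures model with arm, time and arm-by-time. Replace the testing clause in Section 11.4 with a statement that the model-based arm difference in ICIQ-S will be tested and reported with a 95% confidence interval at 7 days and at 4 weeks. If a single test of a difference at either time is preferred, use the joint 2-df test of arm plus arm-by-time. State that the interaction serves only to describe whether the difference changes over time.

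The cost is one sentence. The contrasts come from the same fitted model, with no new data and no change to the sample size.
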